7.5 Followup for Adverse Events

Study personnel will record all reportable events with start dates occurring any time after informed consent is obtained until 7 (for non-serious AEs) or 30 days (for SAEs) after the last day of study participation. At each study visit, the investigator will inquire about the occurrence of AE/SAEs since the last visit. Events will be followed for outcome information until resolution or stabilization.

7.6 Safety Monitoring

All research personnel involved in any way in this project will have completed training in the protection of human research participants per guidelines issued by the United States Department of Health and Human Services, Office for Human Research Protection. The protocol will undergo review and approval by the University of Michigan IRBMED and other necessary regulatory and oversight entities prior to implementation.

We do not expect serious side effects or AEs from this research. AEs that do occur will be reported according to FDA guidelines, and reports will be sent to the University of Michigan IRBMED as required. The Principal Investigator (PI) will be notified when an AE occurs and will determine the attribution and relatedness of each adverse event.

We will also create and work with an independent Data Safety Monitoring Board (DSMB) to monitor safety issues. The DSMB will meet periodically throughout the duration of the study. The DSMB will also report its findings of any adverse events or decisions regarding modification of the protocol to the University of Michigan IRBMED committee.

The study coordinator and project leads will meet monthly with the PI to assess overall study progress, including regulatory matters, recruitment, adverse events, data quality, and to review any interim analyses. Outcomes of these meetings will be reported to the University of Michigan IRBMED on a quarterly basis. All protocols and consent forms are approved by the University of Michigan IRB and reviewed yearly.

Clinical site monitoring is conducted to ensure that the rights and well-being of trial participants are protected, that the reported trial data are accurate, complete, and verifiable, and that the conduct of the trial is in compliance with the currently approved protocol/amendment(s), with International Conference on Harmonisation Good Clinical Practice (ICH GCP), and with applicable regulatory requirement(s). The sponsor clinical monitoring service may conduct periodic on-site reviews of the study, including study initiation visit, periodic site visit and a study closeout visit.

8. INTERVENTION DISCONTINUATION

Discontinuation from SCS will require discontinuation from the study, and remaining study procedures will not be completed. If a clinically significant finding is identified (including, but not limited to changes from baseline) after enrollment, the investigator or qualified designee will determine if any change in participant management is needed. Any new clinically relevant finding will be reported as an adverse event (AE).

Subject participation is strictly voluntary and the research strictly knowledge driven; therefore, a subject may withdraw from further participation in the study without penalty or harm. Any reason(s) the subject may give for terminating his or her participation will be kept confidential. We will store the study documents according to the procedures outlined in Section 11.3 of this protocol. We will require no further information of the subject and the subject will be compensated for his/her completed study visits prior to termination.

Study personnel will be authorized to release a subject from further study participation according to the following guidelines:

- The researcher believes that it is not in the subject's best interest to stay in the study.
- Subject becomes ineligible to participate.
- Subject's condition changes such that he/she needs treatment that is not allowed while taking part in the study.
- Subject does not follow instructions from the researchers.
- The study is suspended or canceled.

Upon termination of a subject, the investigators will ensure the subject is dismissed with any study documents to which he/she is entitled. Subjects will be compensated for their completed study visits prior to termination. Investigators will require no further obligation or participation from a terminated subject.

The reason for participant discontinuation or withdrawal from the study will be recorded on the appropriate Case Report Form (CRF). Subjects who sign the informed consent form and are randomized but do not receive the study intervention may be replaced. Subjects who sign the informed consent form, and are randomized and receive the study intervention, and subsequently withdraw, or are withdrawn or discontinued from the study, will not be replaced.

9. STATISTICAL CONSIDERATIONS

9.1 General Design Issues

We will use descriptive statistics to present participants' demographics and various outcome measures. Categorical data will be presented as frequencies and percentages. Normally distributed continuous data will be presented with means and standard deviations. Non-normal continuous data will be presented with medians and interquartile ranges.

Because this study will employ the crossover design, for inferential tests, we will use linear mixed-effects models to analyze continuous outcomes (e.g., temporal summation, pain intensity on the visual analog scale (VAS)). These models will include a participant-level random intercept to account for correlations of measurements from the same participant. For binary outcomes (e.g., $\geq 50\%$ improvement in VAS scores), we will use mixed effects logistic models. We will obtain the least-squares estimates (e.g., mean temporal summation, mean VAS score, or probability of have a $\geq 50\%$ improvement in VAS) for the treatments and perform group comparisons with the appropriate contrasts. We will establish statistical significance with two-sided $p < 0.05$.

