9.2 Sample Size and Randomization

The primary endpoint will be spinal cord stimulation (SCS)-induced changes in temporal summation (TS). We will calculate TS scores by subtracting the average pain rating of the single-stimulus trials from the average pain rating of the ten-stimuli trials (see Section 9.5.1). If the difference is a positive number, we will conclude that there was pain summation, where larger numbers will indicate increased pain summation or TS. If the difference is zero or a negative number, we will conclude that there was no pain summation or TS. As described in Section 3, we will consider four types or factor levels of SCS: Burst-SCS, KHFSCS, 50 Hz SCS, and Sham SCS. We will consider a repeated-measures design in which all four levels are tested in each participant. We will employ linear mixed-effects models in our analysis. Therefore, our null hypothesis will be that the group means with regards to TS are all equal. Our alternate hypothesis will be that the not all of the group means of TS are equal. If we can reject the null

hypothesis, we will perform the appropriate post-hoc analyses to determine specific differences. To determine specific treatment effects, we will perform the following pairwise tests: Burst vs. Sham, 1 kHz vs. Sham, and 50 Hz vs. Sham. These tests do not require an adjustment for multiplicity because they are hierarchical.

We will perform statistical analysis on SCS-induced changes in TS measured by differences in the corresponding TS. For our study, we assumed a sample size of 20 (25 recruited with an attrition rate of 20% that was estimated from prior SCS studies that employed a similar crossover study design^{39,41}), 80% power, and 5% level of significance with two-tailed tests. Using a paired t test, this will allow us to detect a within-subject effect size (i.e., standardized difference score, d_z) of 0.68, reflecting the difference between active and sham SCS. While this study is exploratory, in the most comparable study conducted to date, eight subjects with neuropathic pain underwent SCS.⁶¹ Assuming a correlation value of 0.5 between TS measured in the same subject, the d_z for the effects of “ON” versus “OFF” stimulation was 0.89. A similar effect size in our study will achieve a statistical power greater than 95% with a sample size of 20.

Treatment Assignment Procedures

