First, we will apply 1-2 light “sample” pressures to the participant’s thumbnail to ensure proper thumb positioning. Once the subject’s thumbnail is in the proper position, we will conduct the familiarization procedure. We will apply a series of discrete pressure-pain stimuli to the subject’s left or right thumbnail. After each pressure is released, we will ask the subjects to rate their pain on a VAS or a 0-100 numerical rating scale (NRS), with 0 representing “no pain” and 100 representing “worst possible pain”. If any pressure is intolerable, subjects are allowed to let us know and the pressure will be released immediately. Subjects can also release the pressure themselves by pressing the ‘STOP’ button on their screen. Following familiarization, we will conduct the MAST ascending test, where we will apply an ascending series of discrete pressure stimuli with a duration of 2.5-5 s beginning at 0.25 kg/cm² and increasing in 0.25-0.50 kg/cm² steps to the subject’s opposite thumbnail. We will ask the subjects to rate their pain using a VAS or a 0-100 NRS. Testing is completed when a pain rating >80 using a VAS or a 0-100 NRS is received or after 10 kg/cm² of pressure has been applied. The MAST system will calculate, in kilograms of force, the patient’s pain detection threshold, tolerance, and moderate and high supra-threshold pain values. Following this test, a second series of tolerable pressures (as determined from the MAST ascending test) may be delivered in a random order. Note: This paradigm may require minor modifications during the execution of this protocol. These modifications will not exceed the parameters described above, i.e., maximum pressure intensity will never exceed 10 kg/cm².

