Spinal Segmental Sensitivity. We will assess spinal segmental sensitivity using a manual vibrometer⁶³ and a pressure algometer^{64,65} at the primary pain site (Fig. 9.3). The primary pain site is defined as the area of maximum pain intensity (i.e., the area of worst possible pain) as reported by the patient. If severe hyperalgesia or allodynia prevents testing of the primary pain site, we will select an adjacent, less sensitive pain area. We will also perform testing at mirror sites (site directly opposite to the tested pain site) and/or bilaterally at several control sites (e.g., trapezius, lateral epicondyle, forearm). We will perform testing with the subject resting in a stationary position (e.g., sitting, supine, prone) to reduce the possibility of postural compression of the nerves being tested.

We will use a handheld vibrometer (VSA-3000, Medoc Inc., Ramat Yishai, Israel) with a 1 cm² circular probe (Fig. 9.3A) to deliver vibratory, non-painful stimuli to determine sensitivity to vibration. We will apply an ascending series of vibratory stimuli. Subjects will report the first

sensation of vibration (denoted as vibratory threshold). We will average the vibratory thresholds across two or three consecutive trials at each site separated by intervals of approximately 20 to 60 seconds. We may also apply a random sequence of fixed intensity vibratory stimuli, 1-3 times each, to the individual sites.

[figure not shown]

Figure 9.3. Spinal segmental sensitivity assessed using a (A) Vibrometer and a (B) Algometer. TS is assessed using a (C) PinPrick stimulator.

We will use a handheld, analog pressure algometer (FPK Algometer, Wagner Instruments, Greenwich, CT) with a 1 cm² flat rubber probe (Fig. 9.3B) to deliver pressure-pain stimuli. We will increase the pressure at a rate of approximately 0.30 kg/cm² or 30-50 kPa/s (100 kPa/s maximum rate), to a maximum of 10 kg/cm². Subjects will report their first sensation of pain (pressure-pain detection threshold) and pressure-pain tolerance. We will average the pressure-pain thresholds and pressure-pain tolerance across two or three consecutive trials at each site separated by intervals of approximately 20 to 60 seconds. We may also apply a random sequence of fixed intensity pressures, 1-3 times each, to the individual sites. We will ask the subjects to report the pain intensity of the pressure stimuli using a VAS or a 0-100 NRS.

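### Pressure measures stop at 10 kg/cm² but have no censoring rule in the planned linear mixed model, so a rise under active SCS is understated to the extent that readings reach the cap (exploratory outcomes only)

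*Combined protocol and SAP*

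**What the plan says.** - **Cap, MAST.** Section 9.5.2 (Generalized Mechanical Sensitivity) ends the ascending series at a pain rating above 80 "or after 10 kg/cm² of pressure has been applied". The MAST system itself calculates pain threshold, tolerance and the supra-threshold values.
- **Cap, algometer.** Section 9.5.2 (Spinal Segmental Sensitivity) raises pressure "to a maximum of 10 kg/cm²". Threshold and tolerance are each averaged over two or three trials per site.
- **CPM.** Section 9.5.2 defines conditioned pain modulation as the difference between pressure-pain thresholds before and after conditioning. A zero or positive difference counts as no response.
- **Model.** Section 9.1 states that "we will use linear mixed-effects models to analyze continuous outcomes", with a participant random intercept. TS and VAS pain are its examples. Section 9.6 names no other model for the pressure measures.
- **Direction.** Section 9.6 (Exploratory analyses) expects lower pressure-pain sensitivity in responders, which means higher thresholds.
- **Status.** Section 9.5.2 makes every outcome other than TS exploratory.
- **Data checks.** Section 10.3.3 flags only values outside an outcome's possible range. A recorded 10 would pass.

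No section says what is recorded when 10 kg/cm² is reached without a report, or how such a trial enters the average or the CPM difference.

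**The concern.** A reading stopped by the device limit is right-censored: the true value lies above 10 by an unknown amount. An ordinary linear mixed model has no place for that information. If 10 is entered, the model takes it as exact.

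The limit also lies on the side of the hypothesised change. If active SCS does raise pressure thresholds, active periods reach the limit at least as often as sham, and the difference shrinks. Aim 1 relies on these static measures to describe mechanism, so a shrunken difference could be read as absence of an effect. Without a flag, a true 10 and a value above 10 may be impossible to tell apart afterwards.

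The safety limit itself is not in question, only how readings at the limit are recorded and analysed.

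**Working it through.** **1. The plan's own figure.** Section 9.2 has "we assumed a sample size of 20" with "80% power, and 5% level of significance with two-tailed tests", and says "this will allow us to detect a within-subject effect size (i.e., standardized difference score, d_z) of 0.68". The exact two-sided paired t test gives 82.2% power at n = 20 and d_z = 0.68; n = 19 already gives 80.04%. At d_z = 0.89 and n = 20, power is 96.5%, in line with "A similar effect size in our study will achieve a statistical power greater than 95% with a sample size of 20". Recruitment also agrees: 20 / (1 − 0.20) = 25. These figures reproduce closely and concern TS only.

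**2. Estimated rise when capped values are entered as 10.** With complete balanced data, the random-intercept model's contrast equals the difference in treatment means. For normal X with mean μ and SD σ, cap c = 10 and a = (c − μ)/σ:

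E[min(X, c)] = μΦ(a) − σφ(a) + c[1 − Φ(a)]

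Example with sham mean 7, SD 3 and a true rise of 1.0:
- Sham: a = 1.000, so 7 × 0.8413 − 3 × 0.2420 + 10 × 0.1587 = 6.750.
- Active (mean 8): a = 0.667, so 8 × 0.7475 − 3 × 0.3194 + 10 × 0.2525 = 7.547.
- Estimated rise: 7.547 − 6.750 = 0.797.

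The documents give no mean or SD for any pressure measure, so all the means and SDs here are assumed:

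| Sham mean, SD | Sham capped | Active capped | Recorded sham mean | Recorded active mean | Estimated rise (true 1.0) |
|---|---|---|---|---|---|
| 4, 2 | 0.1% | 0.6% | 3.999 | 4.996 | 0.997 |
| 5, 2.5 | 2.3% | 5.5% | 4.979 | 5.942 | 0.963 |
| 6, 3 | 9.1% | 15.9% | 5.873 | 6.750 | 0.877 |
| 7, 3 | 15.9% | 25.2% | 6.750 | 7.547 | 0.797 |
| 8, 3 | 25.2% | 36.9% | 7.547 | 8.237 | 0.691 |

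The table treats single readings. An average of two or three trials is affected through whichever of its trials are capped.

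**3. The same question by share at the cap.** Assumed: bivariate normal latent values, latent d_z = 0.68, within-person correlation 0.5 (section 9.2 uses 0.5 for TS; it is borrowed here), n = 20, paired t test.

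| Sham values at cap | Estimate as share of true effect | Power |
|---|---|---|
| 0% | 100% | 82% |
| 1% | 97.5% | 82% |
| 5% | 90% | 80% |
| 10% | 82% | 78% |
| 20% | 69% | 71% |
| 30% | 57% | 64% |
| 50% | 37% | 48% |

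With correlation 0.8, the shares of the true effect for 1%, 5%, 10%, 20%, 30% and 50% at the cap are 98%, 92%, 86%, 73%, 62% and 42%.

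**4. Does a censored model work at this size?** A random-intercept Tobit model was simulated with 20 participants, four conditions, single readings and a fixed cap (150 replicates per setting). Its median estimate was 97–102% of the true effect with 5–50% of sham values capped.

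**5. Can it be applied to the algometer average?** Suppose any average containing a capped trial is treated as censored at that average. The censoring point then depends on the uncapped trials and so on the outcome itself. A simulation with 8,000 participants, three trials, true rise 1.0, visit SD 1.0 and trial SD 1.0–1.5 gave estimates of 1.02 at mean 5, 1.04 at mean 6, 1.03–1.14 at mean 7 and 1.09–1.19 at mean 8. A second simulation of the same rule gave overstatement of about 1–5% with light capping and 7–15% with heavy capping. Censoring each trial at 10 removes this fault, because the censoring point is then fixed by the device.

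**6. CPM.** If only the conditioned threshold is capped, the recorded change is compressed. If both thresholds are capped and entered as 10, the difference is 10 − 10 = 0, which section 9.5.2 classes as no CPM response.

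**The case against.** - **The share at the cap is unknown.** A reader might infer that the rise will be cut off and the effect will be understated. The documents do not support that: they give no mean, SD or share at 10 kg/cm². The larger losses above come from assumed means of 6 to 8. The higher rate of capping under active SCS is likewise a consequence of the hypothesis, which section 9.6 states for responders. This objection stands.
- **Some features may limit capping.** The algometer is used first at the area of worst pain, although mirror or control sites are tested too. MAST also stops at a rating above 80. First-pain threshold cannot exceed tolerance in the same trial, so it reaches the cap no more often. These points stand: exposure will differ by measure and site.
- **Entering 10 is not established for MAST.** The system computes the values, and what it returns for a level not reached is not stated. This stands; it is a gap to close, not evidence that the values are right.
- **The linear mixed model is inferred for these measures.** Section 9.1 names only TS and VAS. But they are given as examples of continuous outcomes, and no other model is offered, so the inference is reasonable.
- **Medians protect the description.** Sections 9.1 and 9.6 report medians for non-normal data, and a median is unaffected while fewer than half the values are capped. That does not protect the model contrast.
- **The bias is attenuation only.** With identical distributions under both conditions, capping creates no false difference. This stands.

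**Conclusion.** The gap is real and its consequence is conditional. MAST and algometer readings are right-censored at 10 kg/cm², the planned model does not allow for it, and no rule covers a capped reading. To the extent that readings are capped and entered as 10, a rise under active SCS is understated. The loss is under 3% with about 1% of sham values at the cap, 10–18% with 5–10%, and about 31% with 20% (correlation 0.5). These sizes rest on normal latent values with a common SD.

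Tolerance and high supra-threshold values are at least as exposed as first-pain threshold. CPM is affected if either of its thresholds is capped.

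A reader might also infer that the main result or the sample size is compromised. Neither is. TS uses a fixed 256 or 512 mN probe and a 0–100 rating, so the pressure cap does not touch it, and section 9.2 sizes the trial on TS. Because only exploratory outcomes are involved and the share at the cap is unknown, the change is optional.

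**What to change.** 1. **Record.** On the MAST and algometer forms, including both CPM thresholds, add a tick-box per trial for 10 kg/cm² reached without a report. State what the MAST system returns for a level not reached.
2. **Report.** Tabulate the number of capped readings by treatment, measure and site.
3. **Analyse.** In section 9.6, pre-specify that where any reading is capped, the pressure measures are analysed with a right-censored (Tobit-type) mixed model. Fit it to the individual trials, each censored at 10, with random intercepts for participant and for visit within participant. Where there is only one value per visit, the visit intercept cannot be separated from the residual and drops out. At minimum, present this as a sensitivity analysis beside the planned model. With nothing capped and one value per visit, it reduces to the planned model.
4. **Averages and CPM.** State how a capped trial enters the descriptive average. Do not treat the whole average as censored at its own value. For CPM, model the two thresholds rather than their difference, or state how a capped pair is handled.

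**Cost.** One tick-box per trial and a little more analysis work. The censored model relies on normality above the cap, and that reliance is greatest with heavy capping at n = 20.

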9.2 Sample Size and Randomization

The primary endpoint will be spinal cord stimulation (SCS)-induced changes in temporal summation (TS). We will calculate TS scores by subtracting the average pain rating of the single-stimulus trials from the average pain rating of the ten-stimuli trials (see Section 9.5.1). If the difference is a positive number, we will conclude that there was pain summation, where larger numbers will indicate increased pain summation or TS. If the difference is zero or a negative number, we will conclude that there was no pain summation or TS. As described in Section 3, we will consider four types or factor levels of SCS: Burst-SCS, KHFSCS, 50 Hz SCS, and Sham SCS. We will consider a repeated-measures design in which all four levels are tested in each participant. We will employ linear mixed-effects models in our analysis. Therefore, our null hypothesis will be that the group means with regards to TS are all equal. Our alternate hypothesis will be that the not all of the group means of TS are equal. If we can reject the null

hypothesis, we will perform the appropriate post-hoc analyses to determine specific differences. To determine specific treatment effects, we will perform the following pairwise tests: Burst vs. Sham, 1 kHz vs. Sham, and 50 Hz vs. Sham. These tests do not require an adjustment for multiplicity because they are hierarchical.

We will perform statistical analysis on SCS-induced changes in TS measured by differences in the corresponding TS. For our study, we assumed a sample size of 20 (25 recruited with an attrition rate of 20% that was estimated from prior SCS studies that employed a similar crossover study design^{39,41}), 80% power, and 5% level of significance with two-tailed tests. Using a paired t test, this will allow us to detect a within-subject effect size (i.e., standardized difference score, d_z) of 0.68, reflecting the difference between active and sham SCS. While this study is exploratory, in the most comparable study conducted to date, eight subjects with neuropathic pain underwent SCS.⁶¹ Assuming a correlation value of 0.5 between TS measured in the same subject, the d_z for the effects of “ON” versus “OFF” stimulation was 0.89. A similar effect size in our study will achieve a statistical power greater than 95% with a sample size of 20.

Treatment Assignment Procedures

We will have two research teams. One team will be unblinded and will perform stimulator programming/adjustment, and the other team will be blinded and will perform clinical testing and collect study outcome measures.

Within two months of enrollment, we will randomize subjects to one of six randomly-allocated sequences consisting of the following treatments: burst, 1 kHz, sham, and 50Hz SCS. Subjects will receive each treatment for seven days following one of the six randomly allocated sequences (crossover design) (Fig. 3.1). We will perform testing before randomization and at the end of each seven-day treatment period.

Participants will be blinded during programming. During the stimulator programming session, we will adjust the settings on the subjects' SCS device. We will adjust the settings such that subjects will receive seven days of a specific treatment allocation. To ensure proper blinding during the first three treatment allocations, we will set the stimulation amplitude so that the participants do not feel any stimulation-induced paresthesias. Sham SCS will be performed by setting the amplitude to 0 mA. For some systems, if the stimulation amplitude is decreased to 0 mA, the system will report that the stimulation is OFF and the participants will know that they are not receiving stimulation. For these systems, we will perform sham SCS by setting the stimulation parameters to their minimal values: pulse width (~20 μ s), frequency (~2 Hz), and amplitude (~0.1 mA). Therefore, participants will not experience stimulation-induced paresthesias during Sham SCS. However, during an active treatment allocation, stimulation-induced paresthesias may sometimes occur (usually as a tingling sensation) due to positional changes (e.g., bending, lifting) and/or extreme movement. To minimize the occurrence of these stimulation-induced paresthesias, we will have the participants assume multiple positions (e.g., sitting, standing, supine, prone) during the programming session and ensure that the stimulation amplitude is low enough to avoid stimulation-induced paresthesias in any of these bodily positions. Therefore, the participant experience should be similar for the first three treatments. After completion of the first three treatment allocations, each participant will receive seven days of tonic 50 Hz SCS that will generate paresthesias over their painful areas. While having 50 Hz SCS as the last treatment in all participants may introduce a potential order effect, this treatment will be performed last because patients will likely know that they are receiving active stimulation due to the paresthesias and this design will minimize the chance of breaking the blind during the first three treatment allocations.

Participants will be instructed not to adjust the stimulation settings during each treatment. At the end of each treatment allocation, we will interrogate the participant's implanted stimulator to ensure that the stimulation settings were not altered during the specific treatment

phase. For some systems, patients are given a magnet that can be used to turn the stimulation off in the case of an emergency. For participants with these systems, we will instruct patients to use the magnet, if needed, in the case of emergency. The magnet can be used to turn the stimulation on or off, in the absence of the programmer.

It is possible that during some treatment allocations, such as during Sham SCS, participants may experience insufficient pain relief. If participants complain of significant discomfort and they are considering exiting the study, we will have the unblinded study personnel examine the current treatment allocation to determine if the participant is receiving stimulation settings that vary substantially from their clinical parameters. If necessary, the participant can decide to have the stimulation settings returned to those determined to be effective through standard-of-care programming procedures.

